#### Secondary objectives:

- To evaluate whether TXA mouthwash before the extraction reduces the bleeding during the procedure.
- To evaluate whether TXA mouthwash reduces early and/or delayed bleeding events
- To evaluate whether TXA mouthwash reduces minor, clinically relevant or major bleeding events or reinterventions.
- To evaluate whether TXA mouthwash reduces the number of unplanned NOAC interruptions.
- To evaluate the safety of skipping the dose of the NOAC on the day of the extraction.

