#### Exploratory analyses:

- To investigate the potential relationship between time of last NOAC dose administered prior to the extraction (regardless of specific NOAC type), time of resuming NOAC after the procedure, and bleeding events
- To investigate the potential benefit of TXA in subgroups of patients (molar versus non-molar extraction)

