#### 4.2.2 SECONDARY OUTCOMES

- The procedural bleeding score
- Early and delayed bleeding
- Minor, clinically relevant non-major and major bleeding
- Clinically-relevant bleeding (non-major and major)

EXTRACT-NOAC Version 1.1
Protocol 6 July 2017

- The number of reinterventions
- The number of unplanned NOAC interruptions

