#### 7.3.3 FOLLOW-UP

Follow-up assessment on day 2 (phone call). In case this would be a Saturday, follow-up can be performed on Friday afternoon. In case this would be a Sunday, follow-up can be performed on Monday.

- Date and time of assessment
- Date and time of restarting NOAC
- Did patient use mouthwash day after the extraction: yes/no
- Bleeding assessment:
  - o Blood on pillow, additional gauze, other: yes/no
  - Blood when brushing teeth: yes/no
  - Blood when rinsing with mouthwash: yes/no
  - Date and time of bleeding
  - Unplanned medical contact (by phone, new consultation or hospitalization) with any health care professional (dentist, general practioner, maxillofacial surgeon): yes/no
- In case of unplanned medical contact:
  - o Date and time
  - Reason (adjudicated): bleeding infection death other (specify)
  - Treatment: no treatment oral antibiotics only rinsing with saline hemostasis with gauze - hemostasis with coagulation - removal of false coagulum - new sutures - blood transfusion - hospitalization
- Unplanned interruption of NOAC: yes/no
- AE and SAE assessment

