#### 7.3.4 FINAL STUDY VISIT

Follow-up assessment on day 7 (phone call). In case this would be a Saturday, follow-up can be performed on Friday afternoon. In case this would be a Sunday, follow-up can be performed on Monday.

- Date and time of assessment
- Number of used study drug vials
- Bleeding assessment between day 2 and day 7:
  - o Blood on pillow, additional gauze, other: yes/no
  - Blood when brushing teeth: yes/no
  - Blood when rinsing with mouthwash: yes/no
  - Date and time of bleeding
  - Unplanned medical contact (by phone, new consultation or hospitalization) with any health care professional (dentist, general practioner, maxillofacial surgeon): yes/no
- In case of unplanned medical contact:
  - Date and time
  - o Reason (adjudicated): bleeding infection death other (specify)
  - Treatment: no treatment oral antibiotics only rinsing with saline hemostasis with gauze - hemostasis with coagulation - removal of false coagulum - new sutures - blood transfusion - hospitalization
- Unplanned interruption of NOAC: yes/no
- Any signs or symptoms or established diagnosis of stroke, myocardial infarction, deep vein thrombosis or pulmonary embolism
- Any non-oral bleeding
- AE and SAE assessment

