#### 10.4.3 ANALYSIS OF THE SECONDARY OUTCOME(S)

 The number of all different type of bleeding events, number of reinterventions and number of unplanned NOAC interruptions in the TXA group and placebo group will be compared using the Fisher Exact Test or Chi Square test, depending on the number of events. The effect of treatment will be estimated by the risk difference and presented along with its associated 95% confidence interval.

The procedural bleeding score in the TXA group and placebo group will be compared using the Student ttest of Mann-Whitney U-test, as appropriate. The effect of treatment will be estimated by the difference between treatments and presented along with its associated 95% confidence interval.

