#### 10.4.8 ADDITIONAL SUB-GROUP ANALYSES

A number of exploratory subgroup analyses is planned, for which the study is not powered, including:

- The number of bleeding events in patients who resumed their NOAC treatment within 24 hours after extraction compared to later than 24 hours after extraction, stratified per treatment group.
- Risk factor analysis for bleeding, eg. patient demographics and procedural characteristics

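### Minor: the NOAC restart time is a planned item only at the day-2 call, so patients who restart after that call have no planned restart time for the exploratory resumption-timing objective

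*Combined protocol and SAP*

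**What the plan says.** All references are to the combined protocol and SAP.

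- **Day-2 call (7.3.3):** the list includes "Date and time of restarting NOAC", the date and time of any bleeding, and a yes/no item on unplanned NOAC interruption. A call that falls on a Saturday can be made on Friday afternoon. One that falls on a Sunday can be made on Monday.
- **Day-7 call (7.3.4):** the list goes from the date and time of the assessment to "Number of used study drug vials" and then to bleeding, again with date and time. On the NOAC it asks only "Unplanned interruption of NOAC: yes/no". It has no restart item, and the interruption item has no dates.
- **Instruction on restarting (7.1.2, 7.3.2):** patients are told to resume the day after the extraction, following their usual regimen.
- **Use of restart time:** the exploratory objective in section 3 concerns "time of resuming NOAC after the procedure, and bleeding events". Section 10.4.8 compares patients who "resumed their NOAC treatment within 24 hours after extraction compared to later than 24 hours after extraction", by treatment group. Section 4.2.3 gives the 24-hour split as an example.
- **Use of interruptions:** section 3 has the secondary objective "To evaluate whether TXA mouthwash reduces the number of unplanned NOAC interruptions". The outcome in 4.2.2 is "The number of unplanned NOAC interruptions", and its analysis is in 10.4.3.

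**The concern.** Whether restart time is missing depends on its own value. It is recorded for patients who restart before the first call and has no planned place for those who restart later. Section 2.1 suggests that peak NOAC levels meeting an immature coagulum may trigger bleeding, so the order of resumption and bleeding is what the exploratory objective is about. For a late restarter with a bleed between day 2 and day 7, the bleed has a date and the restart does not. Analysis cannot recover a date that was not collected.

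The list also has no entry for a patient who has not yet restarted. A blank restart date could mean that the patient had not resumed or that the answer was not obtained.

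**Working it through.** The plan gives no figure on this point, and the sample size of 118 per group does not depend on it. The check compares the two call lists with the analyses that use them, and then asks what the first call reveals about the 24-hour split.

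**Step 1. What each use needs.**

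- Actual time of resuming (section 3): needs the restart date and time. These are not planned for anyone who restarts after the first call.
- Within or beyond 24 hours (4.2.3, 10.4.8): needs only the side of 24 hours on which the restart fell.
- Interruptions (4.2.2, 10.4.3): needs the yes/no answers from the two calls. The plan states that the "number of unplanned NOAC interruptions in the TXA group and placebo group will be compared using the Fisher Exact Test or Chi Square test". No restart time enters.

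**Step 2. Hours from extraction to first call.** The documents give no clock hours. I assume extractions at 08-17 h, ordinary calls at 08-18 h and Friday-afternoon calls at 12-18 h. Shortest gap = 24 × days + earliest call − 17. Longest gap = 24 × days + latest call − 8.

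| First call | Days after extraction | Shortest | Longest |
|---|---|---|---|
| Ordinary day-2 call | 2 | 48 + 8 − 17 = 39 h | 48 + 18 − 8 = 58 h |
| Friday extraction, Monday call | 3 | 72 + 8 − 17 = 63 h | 72 + 18 − 8 = 82 h |
| Thursday extraction, Friday-afternoon call | 1 | 24 + 12 − 17 = 19 h | 24 + 18 − 8 = 34 h |

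A patient known not to have restarted at an ordinary or Monday call is already past 24 hours and belongs in the later group without an exact time. Only the moved Friday call can come before 24 hours.

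**Step 3. How often the moved call comes before 24 hours.** This happens when the call's clock time is earlier than the extraction's. With both times uniform over the assumed hours, the favourable area is (17 − 12)² / 2 = 12.5 and the total area is 9 × 6 = 54, so the share is 12.5 / 54 = 23%. This is a share of Thursday-to-Friday time combinations, not of patients. The group is unknown only if the patient has also not yet restarted. For example, with an extraction at 16 h and a call at 14 h the next day, the gap is 24 + 14 − 16 = 22 h. A restart after that call could fall on either side of 24 hours.

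**Step 4. Number of patients.** The documents do not give the share of Thursday extractions, the share of evening doses, or how often bleeding delays a restart. For delays caused by bleeding alone, assume that 10-20% of 236 patients bleed by the first call, which is 24 to 47 patients. If half of them delay the restart past the call, 12 to 24 are affected. If 10% do, 2 to 5 are. The result follows the assumed fraction, so it is not an estimate.

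**The case against.** The strongest case for leaving the plan alone is that the timing analysis is exploratory and, as 10.4.8 says, unpowered; that patients are told to restart on day 1, so most will have done so before an ordinary call; and that the written analysis uses a 24-hour split for which nearly all late restarters can be classified. All of this stands and keeps the point minor. It does not close the gap, because section 3 refers to time of resuming without a cut-point and the 24-hour split in 4.2.3 is only an example.

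A reader might infer four stronger things that the documents do not support.

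- **That the interruption outcome is undermined.** It is a number of interruptions, asked yes/no at both calls, and no planned analysis uses the date or length of one.
- **That the longest delays fall out of the 24-hour comparison.** Step 2 shows the reverse for ordinary and Monday calls, provided that non-restart at the call is recorded.
- **That restart time is never captured.** The CRF itself is not among the documents, and 7.1.1 and 7.3.6 provide for review of the medical file after unplanned medical contact. That review concerns the type of contact, and restart time is not named in it. The supported statement is that there is no planned item.
- **That a dozen or more patients are affected.** The top of that range needs 47 bleeders by the first call. The rates in 10.5 imply (30% + 15%) / 2 = 22.5% of 236, or about 53, through day 7. That would put 47 / 53 = 89% of events before the call, although the pilot study's excess in section 2.1 was in delayed bleeding.

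One might also want every missed day-1 restart counted as an unplanned interruption. That definition is debatable: it would mix forgotten doses and short delays with interruptions caused by bleeding. It is not proposed here.

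**Conclusion.** The point holds as a minor gap in data capture. Patients who have not restarted by the first call have no planned restart time. Among them can be compliant patients with an evening dose whose call was moved to Friday afternoon. For these patients the exploratory objective cannot use the actual time or place a delayed bleed before or after resumption. The 24-hour group is in doubt only when the moved Friday call comes before 24 hours and the patient has not yet restarted. This conclusion rests on the assumed clock hours in step 2. The number affected is not derivable and is probably small, given the day-1 instruction. The primary outcome, alpha, power and the planned secondary test of interruptions are untouched.

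One adjacent weakness can be repaired at the same time. The interruption item has no dates, so a yes at both calls could be one continuing interruption or two separate ones.

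**What to change.** - **7.3.3:** add an explicit entry for a patient who has not yet restarted the NOAC at the time of the call.
- **7.3.4:** repeat the restart date and time for patients who had not restarted at the first call, with an option for not restarted by day 7.
- **7.3.3 and 7.3.4:** add start and stop dates to the interruption item, so that one continuing interruption is not counted twice.
- **10.4.8:** state that patients known not to have restarted by 24 hours are analysed in the later-than-24-hour group.

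These changes affect what is recorded and how it is grouped, identically in both arms, and leave NOAC management as it is. The cost is a few items on calls already planned and one sentence in 10.4.8. The downside is a slightly longer day-7 call.

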#### 7.3.4 FINAL STUDY VISIT

Follow-up assessment on day 7 (phone call). In case this would be a Saturday, follow-up can be performed on Friday afternoon. In case this would be a Sunday, follow-up can be performed on Monday.

- Date and time of assessment
- Number of used study drug vials
- Bleeding assessment between day 2 and day 7:
  - o Blood on pillow, additional gauze, other: yes/no
  - Blood when brushing teeth: yes/no
  - Blood when rinsing with mouthwash: yes/no
  - Date and time of bleeding
  - Unplanned medical contact (by phone, new consultation or hospitalization) with any health care professional (dentist, general practioner, maxillofacial surgeon): yes/no
- In case of unplanned medical contact:
  - Date and time
  - o Reason (adjudicated): bleeding infection death other (specify)
  - Treatment: no treatment oral antibiotics only rinsing with saline hemostasis with gauze - hemostasis with coagulation - removal of false coagulum - new sutures - blood transfusion - hospitalization
- Unplanned interruption of NOAC: yes/no
- Any signs or symptoms or established diagnosis of stroke, myocardial infarction, deep vein thrombosis or pulmonary embolism
- Any non-oral bleeding
- AE and SAE assessment

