#### 4.2 STUDY OUTCOMES

The procedural bleeding score is a visual analogue score (VAS) ranging from 0 (no bleeding) to 10 (unstoppable bleeding).

A reintervention is defined as any procedure in the oral cavity for the treatment of bleeding, performed by any dentist or maxillofacial surgeon, except for rinsing the extraction socket with saline.

All suspected bleeding events and reinterventions will be adjudicated by a blinded adjudicator, unaware of the assigned treatment.

Bleedings are defined as previously published (7):

- Minor bleeding: any oral bleeding experienced by the patient that does not require medical contact.
   Eg. blood on the pillow, bleeding requiring the use of additional gauzes, clear red bleeding when spitting out the mouthwash
- Clinically relevant non-major bleeding: any oral non-major bleeding requiring unplanned medical contact (by phone or with any health care professional (dentist, general practitioner, maxillofacial surgeon), with or without re-intervention
- Major bleeding: any oral bleeding requiring blood transfusion, hospitalization or resulting in death
- Early bleeding: any oral bleeding occurring after the extraction up to and including day 1 after the extraction
- Delayed bleeding: any oral bleeding occurring between day 2 and day 7

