#### Safety outcomes:

- Any non-oral bleeding
- All thrombotic events including myocardial infarction, stroke, systemic embolism and venous thrombo-embolism up to the endo of study follow-up.

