#### 7.3.6 UNSCHEDULED VISIT

In case of unplanned medical contact, the prespecified outcomes will be assessed as planned by phone call, and in addition, additional relevant medical data on the type of unplanned medical contact will be identified from the medical file. All suspected bleeding events and reinterventions will be adjudicated by a blinded adjudicator, unaware of the assigned treatment.

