# 8.3 TIME PERIOD AND FREQUENCY FOR EVENT ASSESSMENT AND FOLLOW-UP

Adverse events will be assessed at day 2 and 7 follow-up.

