#### 8.4 REPORTING PROCEDURES

Following the subject's written consent to participate in the study, all AEs and SAEs, related to the study agent (tranexamic acid, IMP) will be collected.

Although no drugs other than the study agent will be provided by the sponsor to the subjects participating in this interventional study, investigators may become aware of (S)AEs in subjects possibly in relation to marketed drugs as a part of their ongoing therapies. Data on SAEs will be collected, and relatedness of these events to the use of marketed drugs associated with this study (where applicable) will be assessed by the investigator. SAEs determined to be related, including exposure during pregnancy and overdose, will be recorded and reported. A form will be completed for any event where doubt exists regarding its status of seriousness, including overdose and cancer. Reporting of SAEs of marketed drugs will follow regulatory guidelines. Pending on the marketed drug, reconciliation of SAEs cases (case level only) with the manufacturer is indicated. (E.g. for apixaban, frequency of reconciliation is planned every 3 months and

prior to the database lock or final data summary. BMS GPV&E will email, upon request from the Sponsor, Requests the GPV&E reconciliation report. for reconciliation should be [contact]. The data elements listed on the GPV&E reconciliation report will be used for case identification purposes. If the Sponsor determines a case was not transmitted to BMS GPV&E, the case will be sent immediately to BMS. For apixaban, BMS will be contacted at [contact] for SAE. Adverse Events of special interest for apixaban include potential or suspected cases of liver injury, including but not limited to liver test abnormalities, jaundice, hepatitis or cholestasis, regardless of whether the events are classified as serious or unexpected.)

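### The only dedicated thrombotic item merges symptoms with diagnoses, omits systemic embolism, and falls outside the stated blinded adjudication, so unconfirmed reports could enter the safety counts

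*Combined protocol and SAP*

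**What the plan says.** The safety outcome in section 4.2.2 is "All thrombotic events including myocardial infarction, stroke, systemic embolism and venous thrombo-embolism up to the endo of study follow-up". No diagnostic criteria are given.

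Section 7.3.4 describes the final contact as "Follow-up assessment on day 7 (phone call"). Its item on thrombosis reads "Any signs or symptoms or established diagnosis of stroke, myocardial infarction, deep vein thrombosis or pulmonary embolism". The day-2 call in section 7.3.3 has no equivalent item.

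On confirmation, section 4.2 states "All suspected bleeding events and reinterventions will be adjudicated by a blinded adjudicator, unaware of the assigned treatment", and section 7.3.6 repeats this. Neither place mentions thrombotic events.

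Two other routes exist:

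- **Adverse events.** Section 8.3 says "Adverse events will be assessed at day 2 and 7 follow-up", and both call forms carry an AE and SAE line. Section 8.4 opens by saying that "all AEs and SAEs, related to the study agent (tranexamic acid, IMP) will be collected", then adds more broadly "Data on SAEs will be collected, and relatedness of these events to the use of marketed drugs associated with this study" will be assessed.
- **Unplanned contact.** Both calls ask about unplanned medical contact, including hospitalisation, and record an adjudicated reason (bleeding, infection, death or other). After such a contact, section 7.3.6 says that "additional relevant medical data on the type of unplanned medical contact will be identified from the medical file".

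The counts are used twice: in the TXA versus placebo comparison by Fisher or chi-square test (section 10.4.4) and in the safety review after 100 patients (sections 8.5 and 10.4.7.1). They are also the natural data for the secondary objective in section 3 on the safety of omitting the NOAC dose on the day of extraction.

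**The concern.** The outcome is an event, but the item is positive for a symptom. A form filled in exactly as written cannot show whether a positive entry is a swollen leg that nobody examined or a deep vein thrombosis confirmed in hospital. It also gives no prompt for a systemic embolism that the outcome definition counts.

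True thrombotic events over seven days in 236 patients are likely to be few, so a small number of unconfirmed reports could make up much of the total. That would raise the pooled rate seen at the safety review and used for the dose-omission objective, and it would dilute any real difference between the arms.

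**Working it through.** **Step 1. Outcome against data collection**

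| Element | Outcome (4.2.2) | Day-7 item (7.3.4) |
|---|---|---|
| Myocardial infarction | included | included |
| Stroke | included | included |
| Venous thrombo-embolism | included | included, as its two usual forms |
| Systemic embolism | included | absent |
| What is recorded | event | symptom or diagnosis, one entry |
| Stated blinded confirmation | none (4.2 and 7.3.6 name bleeding and reinterventions) | none |

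**Step 2. Do the other routes close the gap?**

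- The AE and SAE assessment is made on the same two calls. The first sentence of section 8.4 limits collection to events related to the study agent, while sections 7.3.3, 7.3.4 and 8.3 carry no such limit. Section 8.2.2 adjudicates the relationship to study drug, not whether the event occurred.
- File review follows an unplanned medical contact, and the stated way of learning about that contact is the call. Thrombosis could be written under the reason other, but it is not a listed reason. A patient with symptoms and no contact triggers no verification.
- No procedure is stated for a patient who cannot be reached by phone. Section 7.3.5 (early termination visit) is marked not applicable, and section 5.4.2 continues the same calls after withdrawal.

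The routes are real but partial.

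**Step 3. Size, for illustration only**

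The plan has no figure for thrombotic events to reproduce. The denominators come from section 10.5: 118 per group, 236 in total. That number follows from 30% v 15%, two-sided 5%, 80% power and unpooled variance: (1.960 + 0.842)² × (0.30 × 0.70 + 0.15 × 0.85) / 0.15² = 117.7, rounded up to 118. It does not depend on this point.

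*Share of false entries.* Assume a true 7-day risk t of 0.2% to 1%, and a proportion f of 0.5% to 5% of the remaining patients who report a symptom without a diagnosis. Neither range is in the documents.

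- True events: 236 × t = 0.5 to 2.4.
- Unconfirmed reports: 236 × (1 − t) × f = 1.2 to 11.8.
- Share unconfirmed: (1 − t)f / [t + (1 − t)f]. At t = 1%, f = 0.5%: 0.00495 / 0.01495 = 33%. At t = 0.2%, f = 5%: 0.0499 / 0.0519 = 96%.

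*Pooled rate with no true event* (exact 95% intervals):

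| Positive entries | Rate | 95% CI |
|---|---|---|
| 0/236 | 0% | 0 to 1.6% |
| 2/236 | 0.8% | 0.1 to 3.0% |
| 5/236 | 2.1% | 0.7 to 4.9% |
| 12/236 | 5.1% | 2.7 to 8.7% |
| 0/100 (at the safety review) | 0% | 0 to 3.6% |
| 3/100 (at the safety review) | 3.0% | 0.6 to 8.5% |

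*Comparison of arms* (Fisher, two-sided, 118 per arm). A split of 5 v 0 gives p = 0.060 and 6 v 0 gives p = 0.029, so single reports matter. If a true 6 v 0 is joined by one false report in each arm (7 v 1), p becomes 0.066; with two in each arm (8 v 2), it becomes 0.10.

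**The case against.** The strongest reply is that the item reads naturally as a sensitive screening prompt. Sections 8.5, 10.4.4 and 10.4.7.1 speak of thrombotic events or complications, and nothing says that a symptom alone is counted. This stands: the plan leaves the counting rule open and does not set a wrong one. A reader might infer that symptom reports will count as events, but the documents do not say so.

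A reader might also infer that the outcome rests on a single phone item and is never adjudicated. That goes too far. AEs and SAEs are assessed at both calls, and a fatal, life-threatening or hospitalised event meets the SAE definition in section 8.1.2. Unplanned contact has an adjudicated reason that includes death and other, with file review. The narrower statement survives: no adjudication specific to thrombosis is stated, and these routes depend on the same calls.

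A third tempting reading is that patients too ill to answer are missed. The forms have fields for death and hospitalisation, so some information from elsewhere is evidently foreseen. Without a proxy or record-check procedure this is a risk, not a stated consequence.

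Finally, the trial is double-blind, so false reports should fall largely evenly between the arms, and the safety review has no threshold for them to cross. This also stands. Even noise should not by itself create a difference between the arms. It can still dilute a real one and inflate the pooled rate.

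**Conclusion.** The point holds as a moderate gap in a safety outcome. Three facts rest on the text alone: symptoms and diagnoses share one entry, systemic embolism is in the outcome but not in the item, and the stated blinded adjudication does not extend to thrombotic events. It follows that unconfirmed symptom reports could enter the counts used in sections 8.5, 10.4.4 and 10.4.7.1.

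The size is not established. The 33% to 96% range, the pooled rates and the dilution example rest on assumed symptom and event rates, and on counting every positive entry. They show only that a few reports would matter at this sample size.

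**What to change.** - **Section 7.3.4:** split the item into symptoms and established diagnosis, and add systemic embolism.
- **Sections 4.2 and 7.3.6:** extend the existing blinded adjudication to all suspected thrombotic events, using the medical file.
- **Sections 10.4.4 and 10.4.7.1 (with 8.5):** state that only confirmed thrombotic events are counted; unconfirmed symptom reports can be listed separately.
- **Section 8.4:** reconcile with sections 7.3.3, 7.3.4 and 8.3 on whether all AEs and SAEs are collected or only related ones.
- **Optional:** state that the hospital file is checked for any patient not reached at day 7. The yield is less certain, because care outside the two hospitals may not appear there.

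The cost is one form change, a few file look-ups and a few extra cases for the adjudicator already in place. The sample size and the primary analysis do not change.
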